5.4.4 Interim Analysis for Efficacy

Following the end of Season 2, if the predicted total number of per-protocol cases for the primary endpoint as estimated in [Section 5.4.3](#) is less than [REDACTED] cases, and if at least [REDACTED] per-protocol influenza cases meeting the primary endpoint have occurred (ie, at least [REDACTED] information time), an interim analysis for efficacy is planned to be conducted by an independent statistician and reviewed by the IDMC during Season 3.

If either of the 2 conditions is not met, the proposed interim analysis for efficacy will not be performed and the alpha will not be adjusted at the final analyses.

The data cleaning for this interim analysis if conducted will focus on critical data for vaccine efficacy assessment involved in analysis sets and primary endpoint definitions: protocol deviations, ILI occurrence, and laboratory results.

At the interim analysis, the primary objective and first secondary objective will be assessed using

- the statistical methods described in [Section 5.1.1.2](#) to demonstrate the primary and first secondary objectives. Note: fixed one-sided alpha of [REDACTED] will be used regardless of the observed total number of evaluable cases at the time of interim analysis, and the overall Type I error is not inflated ([Appendix 1. Overall Type I error using a fixed alpha value for interim efficacy analysis](#)).
- the predictive power as described below in [Section 5.4.4.1](#) for the probability to demonstrate these objectives at the end of the ongoing Season 3 based on the and at the end of the study (ie, with [REDACTED] evaluable cases for the primary endpoint).

The IDMC may recommend stopping the study at the end of Season 3 if the primary and first secondary objectives are demonstrated (ie, the stopping rule for superior efficacy is fulfilled), if there is a high probability to demonstrate these objectives at the end of Season 3, or for futility if the probability to demonstrate the primary objective at the end of study is too low. In any case, the study will not stop before the 3 influenza seasons are completed. The IDMC will inform the Sponsor Executive Board of the recommendation, and then the Executive Board makes decision for stopping or not, taking the epidemiology data and relevant external data if available into account. In particular, a stopping for futility recommendation from the IDMC is a guideline that may or may not be followed depending on the totality of the available interim results. Therefore, the futility rule is not binding to the conduct and conclusion of the study ([18](#)).

The clinical study team will not be made aware of the IDMC's recommendations until the final database lock and unblinding at the end of Season 3. The clinical study team, the investigators, and study subjects will remain blinded until the end of the study. In addition, no modification will be allowed to the study conduct after this interim analysis. Information on organizational aspects, roles, responsibilities, data flow, and communication with the IDMC will be detailed in the IDMC charter.

In addition, at the time of the interim analysis, other efficacy and safety objectives may be assessed on the available data for information. These will be detailed in a separate SAP for the IDMC.

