If the interim analysis is conducted, an alpha spending method quoted by Lan and Demets (power family, $\phi=2$) will be used to maintain an overall Type I error (the 'alpha') of 0.025 one-sided, considering that [REDACTED] of information time is reached at the time. Consequently, a one-sided nominal alpha of [REDACTED] will be used at interim and final analysis, respectively. This corresponds to [REDACTED] two-sided CIs to be used at interim and final analysis, respectively. If the interim analysis is not conducted or if the superior rVE is concluded at the interim analysis with the most stringent [REDACTED] threshold (ie, the stopping rule for superior efficacy is fulfilled), the final analysis will be performed with one-sided alpha of 0.025 without multiplicity adjustment.

A complementary analysis of comparing Kaplan-Meier curves between QIV-HD and QIV-SD groups for the primary endpoint will be performed for all subjects and stratified by age group and previous vaccination history:

- Start date: D0 (first vaccination date)
- Event date for subjects with a protocol-defined ILI is the start date of the first fever episode
- End date for subjects without a protocol-defined ILI is the last visit or contact date whichever is later

The non-inferiority test on the FASE and the superiority test on the PPASE will be performed as sensitivity analyses.

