The sample size needed for the assessment of the primary objective of the study is expected to be approximately █ subjects and may be adjusted based on the blinded number of cases in order to maintain the likelihood of achieving approximately █ evaluable influenza cases from the PPASE meeting the primary endpoint.

These required numbers of evaluable influenza cases would provide at least █ power at final analysis to conclude on the primary objective under the following assumptions:

- The true rVE of QIV-HD to QIV-SD is █
- An overall one-sided Type I error rate 0.025 (█ spent at interim and final analysis, respectively)
- The lower bound of the CI of rVE should be > 5%
- An allocation ratio of QIV-HD to QIV-SD of 1:1
- An overall influenza attack rate of █ for the occurrence of an influenza case in the QIV-SD group (equivalent to an attack rate of █ across QIV-HD and QIV-SD groups in the PPASE given total number of evaluable cases is █)
- █ of enrolled subjects evaluable for the primary endpoint

Based on the same assumptions and using a more stringent █ threshold, the power for the first secondary objective at final analysis is expected at approximately █

If there is a need to extend the study to Season 4, number of subjects required will be re-calculated in a blinded manner. By way of illustration,

If the overall attack rate across 2 vaccine groups is █, to demonstrate the superior efficacy of QIV-HD over QIV-SD with the lower bound of █ CIs > █ and approximately █ power assuming the true rVE of QIV-HD to QIV-SD is █, 1:1 allocation ratio and █ of enrolled subjects evaluable the total number of subjects required is █. Additional █ subjects will be enrolled in Season 4. At the end of Season 4, █ cases would be expected to have occurred.

At least █ evaluable laboratory-confirmed influenza cases will be required for the interim analysis to be conducted. Such a number of cases would provide a power of approximately █,

to demonstrate up to the first secondary objective if the vaccine efficacy is [REDACTED] respectively, using one-sided alpha of [REDACTED].

For the assessment of the 2nd and 3rd confirmatory secondary efficacy objectives, the assumptions will be similar to those for primary objective except

- The lower bound of the CI for the corresponding rVE will be superior to 0%.

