Appendix 1. Overall Type I error using a fixed alpha value for interim efficacy analysis

An alpha spending method quoted by Lan and Demets (power family, phi=2) is used to maintain an overall Type I error (the ‘alpha’) of 0.025 one-sided, assuming [REDACTED] of information time is reached at the time of interim analysis. Consequently, one-sided nominal alpha values of [REDACTED] at interim and [REDACTED] at final analysis (corresponding to [REDACTED] two-sided CIs respectively) are used for the sample size calculation as detailed in [Section 5.5.1](#).

At the time of interim analysis if conducted, fixed one-sided alpha value of [REDACTED] will be used regardless of the observed total number of evaluable cases. The overall Type I error is not inflated using fixed alpha value at interim analysis as demonstrated in the following.

Let x_v^1, x_c^1, x_T^1 denote the observed number of cases at interim analysis in vaccine, control and both groups ($x_T^1 = x_v^1 + x_c^1$) and let n_v^1, n_c^1 denote the number of subjects in vaccine and control groups at interim analysis. Similarly, let x_v^2, x_c^2, x_T^2 denote the future number of new cases to be observed in the remaining part of the study and let n_v^2, n_c^2 denote the number of subjects in vaccine and control groups in the remaining part of the study. Assuming the number of cases in vaccine group is binomially distributed conditionally on the total number of cases at the interim analysis and for the remaining of the study, ie, $X_v^1 \sim B(q, x_T^1)$, $X_v^2 \sim B(q, x_T^2)$

Given that $VE = 1 - \frac{x_v^1/n_v^1}{x_c^1/n_c^1} = 1 - \frac{(x_v^1+x_v^2)/(n_v^1+n_v^2)}{(x_c^1+x_c^2)/(n_c^1+n_c^2)}$, and in this study $n_v^1 = n_c^1, n_v^2 = n_c^2, q = \frac{x_v^1}{x_v^1+x_c^1} = \frac{x_v^1+x_v^2}{x_v^1+x_v^2+x_c^1+x_c^2} = \frac{1-VE}{2-VE}$

$$Pr(X_v^1 = x_v^1 | q, x_T^1) = C_{x_T^1}^{x_v^1} q^{x_v^1} (1-q)^{x_c^1} \quad (1)$$

$$Pr(X_v^2 = x_v^2 | q, x_T^2) = C_{x_T^2}^{x_v^2} q^{x_v^2} (1-q)^{x_c^2}$$

$$Pr(X_v^1 + X_v^2 = x_v^1 + x_v^2 | q, x_T^1 + x_T^2) = C_{x_T^1}^{x_v^1} q^{x_v^1} (1-q)^{x_c^1} C_{x_T^2}^{x_v^2} q^{x_v^2} (1-q)^{x_c^2} \quad (2)$$

Based on the above formula, the overall Type I error to reject the null hypothesis ($H_0: rVE \leq VE_0$) at the interim analysis and at the end of the trial where VE_0 is the pre-specified superiority margin, is obtained as follow:

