1. Compute [REDACTED] two-sided confidence interval of rVE (ie, one-sided alpha of [REDACTED] for the interim analysis) for every combination of (x_v^1, x_c^1) .
2. If the lower bound of the confidence interval of rVE is greater than VE_0 , for the considered combination the null hypothesis is rejected.
3. The Type I error at the interim analysis is then the sum of the probability calculated in equation (1) over the set of all combination of cases for which the null hypothesis is rejected.
4. Compute [REDACTED] two-sided confidence interval of rVE (ie, one-sided alpha of [REDACTED] for the final analysis at the end of the study) for every combination of $(x_v^1 + x_v^2, x_c^1 + x_c^2)$.

5. If the lower bound of the confidence interval of rVE as calculated in step 1 is less than or equal to VE_0 and the lower bound of the confidence interval as calculated in step 4 is greater than the pre-specified margin, for the considered combination of $(x_v^1, x_c^1, x_v^2, x_c^2)$ the null hypothesis is rejected.
6. The Type I error at the final analysis is then the sum of the probability calculated in equation (2) over the set of all combination of cases for which the null hypothesis is rejected as in step 5.
7. The overall Type I error for the study is the sum of Type I error at the interim and final analyses.

Table 7.1 details the calculated overall Type I error for the study using fixed alpha values of [REDACTED] at the interim analysis and [REDACTED] at the final analysis based on total number of evaluable cases available at interim analysis increasing from [REDACTED]

Table 7.1: The overall Type I error using fixed alpha values

Overall Type I error

Total number of cases at interim

Information time (%)

rVE=5% and
VE₀=5%

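### The final nominal alpha is fixed from one planned information time and is not tied to the actual final case count, so overall Type I error can slightly exceed 0.025 if Season 4 brings more cases than planned

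*SAP*

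**What the plan says.** SAP 5.1.1.2 (and Protocol 12.1.1.2) invokes "an alpha spending method quoted by Lan and Demets", power family with phi=2, at one assumed information time, and derives one interim and one final one-sided nominal alpha from it. Appendix 1 repeats this: the method "quoted by Lan and Demets (power family, phi=2) is used to maintain an overall Type I error" of 0.025, assuming that a blacked-out share "of information time is reached at the time of interim analysis".

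The interim level is then held fixed. SAP 5.4.4 states that it "will be used regardless of the observed total number of evaluable cases at the time of interim analysis", and Appendix 1 likewise that it "will be used regardless of the observed total number of evaluable cases". The final level is also a single value. It reverts to 0.025 in two cases only: no interim is held, or the superior-efficacy stopping rule was met at the interim (SAP 5.1.1.2, 5.4.4). SAP 5.1.2.2 applies the same pair of levels to the first secondary objective. No text links the final level to the number of cases at the final analysis.

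Appendix 1 supports its statement of no inflation with Table 7.1, which "details the calculated overall Type I error for the study using fixed alpha values of" two redacted values, "based on total number of evaluable cases available at interim analysis increasing from" a redacted minimum. The visible text describes no variation of the final total.

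**The concern.** The final nominal level in a two-look design depends on the correlation between the looks, which is set by the ratio of interim to final cases. A spending approach normally keeps the alpha already spent and solves the last boundary from the actual ratio. The SAP cites the approach but leaves out that last step.

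The final count is the less certain of the two. The interim is run only if Season 3 is forecast to fall short (SAP 5.4.4), so the study either ends at Season 3, probably below plan, or goes on to Season 4. Season 4 is sized by number of subjects, with an expected number of cases (SAP 5.5.1), and surveillance closes on a calendar date (SAP 3.2). Nothing caps the cases. SAP 5.4.3 says that blinded re-estimation leaves Type I error controlled, but it does not discuss boundaries computed for a different ratio.

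At stake are a small excess over 0.025 if cases overshoot and some unused alpha if they fall short.

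**Working it through.** **Inputs from the documents.** "An overall one-sided Type I error rate 0.025" (SAP 5.5); power-family spending with phi=2 (Appendix 1); superiority margin of 5% and the exact conditional binomial CI (SAP 5.1.1.2); 1:1 allocation (SAP 5.5.1).

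**Assumed, because the values are blacked out.** Planned information time t = 0.5 to 0.8; planned totals of 300 to 1,200 cases for the exact calculation; interim held exactly at its minimum count unless stated. Table 7.1 cannot be reproduced, since its entries and inputs are redacted.

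**Step 1: levels at plan.** Interim alpha a1 = 0.025 × t². Final alpha a2 solves P(Z1 > c1) + P(Z1 ≤ c1, Z2 > c2) = 0.025, with correlation √t. For t = 0.7, a1 = 0.025 × 0.49 = 0.01225 and a2 = 0.0197.

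**Step 2: the SAP's own statement.** With the final total at plan and the interim count 5-20% above its minimum, the normal approximation gives an overall error of 0.0209-0.0248. The claim of no inflation is right there.

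**Step 3: vary the final count.** Hold a1 and a2 fixed and set the correlation to √(t/f), where f = actual final cases / planned final cases. For t = 0.7 and f = 1.2 the ratio is 0.7/1.2 = 0.583 and the total is 0.0264.

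| t | a1 | a2 | f=0.85 | f=0.90 | f=1.10 | f=1.20 | f=1.50 |
|---|---|---|---|---|---|---|---|
| 0.5 | 0.00625 | 0.0218 | 0.0244 | 0.0246 | 0.0253 | 0.0255 | 0.0260 |
| 0.6 | 0.0090 | 0.0208 | 0.0240 | 0.0244 | 0.0255 | 0.0259 | 0.0267 |
| 0.7 | 0.01225 | 0.0197 | 0.0232 | 0.0239 | 0.0258 | 0.0264 | 0.0276 |
| 0.8 | 0.0160 | 0.0187 | 0.0216 | 0.0231 | 0.0263 | 0.0272 | 0.0289 |

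**Step 4: exact test.** Appendix 1's two-stage enumeration was run at rVE = 5%, so q = 0.95/1.95 = 0.487. Discreteness pulls most overshoot settings below 0.025. Some exceed it:
- t=0.8, 1,200 planned cases: 0.0261 at f=1.2 and 0.0284 at f=1.5
- t=0.8, 800 planned: 0.0282 at f=1.5
- t=0.6, 500 planned: 0.0262 at f=1.5

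Over 400-800 planned cases, t = 0.5-0.8 and finals 15-50% above plan, about 22% of settings exceed 0.025 with fixed levels, and none do once the final level is recomputed.

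**Step 5: shortfall.** Over 400-800 planned cases and t = 0.5-0.7, mean exact alpha is 0.0225 with the final total at plan. It is 0.0210 with finals at 75-90% of plan and fixed levels, and 0.0223 after recomputing. So recomputing recovers 0.0223 − 0.0210 = 0.0013. The gap at plan, 0.025 − 0.0225 = 0.0025, is discreteness and has nothing to do with fixed levels. For power, with finals at 85-95% of plan, the median gain is zero and about 72% of settings gain nothing.

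**Step 6: re-solved final levels (normal approximation).** For t = 0.7: 0.0219 at f=0.85, 0.0210 at f=0.90, 0.0187 at f=1.10 and 0.0180 at f=1.20, against 0.0197 at plan.

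**The case against.** The strongest reply is that the SAP's explicit statement is correct as far as it goes: a fixed interim alpha does no harm when the interim count varies, and the fix keeps that rule. A reader might infer from the quoted sentence that the interim alpha itself inflates the error. The documents do not support that.

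The excess is also small and conditional. It needs an interim-to-final ratio below the planned one. The SAP requires at least the minimum count, so an interim above it offsets an overshoot. With finals 15-30% above plan and t = 0.5-0.7, about 9% of exact settings exceed 0.025 when the interim is at its minimum. If the interim is 10% above it, about 2% do, with a maximum of 0.0252. Season 4 is sized towards a target, so a large overshoot is not what is planned.

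A second tempting reading is that fixed levels cost real power when Season 3 ends short. The largest gain found, from 46.6% to 50.4%, is a corner case: 400 planned cases, t = 0.7, final 300, true rVE 25%, so 0.7 × 400 = 280 of the 300 final cases are already in at the interim. With 305 final cases both methods give 50.1%. Nor is raising the level clearly free, because stopping at Season 3 can depend on predictive power and therefore on the interim result. Under assumed rules, the normal approximation gives an overall error of about 0.025-0.027 with fixed levels and 0.025-0.028 with recomputed ones.

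All of this stands. It limits the size of the point but does not fill the missing step.

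**Conclusion.** The point holds as a minor gap concerning the final level only. The plan fixes that level from one planned information time, and the visible check does not cover a final count that differs from plan. An overshoot with the interim near its minimum can take the overall one-sided error slightly above 0.025, by the amounts in Steps 3 and 4. A shortfall makes the test mildly conservative, with little or no power to recover. Nothing is lost when no interim is held or the superior-efficacy rule is met, since the final alpha is then 0.025.

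Every figure depends on assumed information times and case totals. Table 7.1 cannot be read, so it would be wrong to conclude that the SAP's statement of no inflation is false. What can be said is that its visible support does not extend to a varying final count.

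**What to change.** Keep the fixed interim alpha. State in SAP 5.1.1.2 and Appendix 1 that the final nominal level, and the matching CI level, is computed from the actual interim and final case totals, with the Lan-DeMets function or Appendix 1's enumeration, so that total alpha does not exceed 0.025. Lower the level when the final count exceeds plan. Raise it for a shortfall only if the enumeration, including the rule for stopping at Season 3 on predictive power, still totals at most 0.025; otherwise keep the planned level. Carry the same level to the first secondary objective in SAP 5.1.2.2, and record the change in SAP 5.7, since Protocol 12.1.1.2 gives the same fixed pair.

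The cost is about one paragraph and no change to design or conduct. The downside is a slightly wider final CI if cases overshoot. In the example with t = 0.7 and f = 1.2, the two-sided level moves from 1 − 2 × 0.0197 = 96.06% to 1 − 2 × 0.0180 = 96.40%.

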5.4.4.1 Predictive Power

Bayesian predictive power (19) with the non-informative uniform prior [Uniform (0, 1)] will be used for the calculation of the probability, conditional on the interim results, to conclude at the end of Season 3 and at the end of study. The Bayesian posterior distribution is determined using the results of interim analysis (likelihood data assuming the number of cases in QIV-HD group is binomially distributed conditional to the total number of cases in both vaccine groups) combined with the uniform prior distribution. Detailed statistical method for the predictive power is in [Appendix 2. Bayesian Predictive Power](#).

If the superiority based on the [REDACTED] margin is not demonstrated at the interim analysis, the predictive power at the end of Season 3 will be calculated based on the predicted total number of per-protocol cases for the primary endpoint at the end of Season 3 using the available data at the time of interim analysis (Note: this total number of cases may be different from the trigger for the planning of extension to Season 4), the lower bound of the CI of rVE for the primary endpoint > [REDACTED] and one-sided alpha of [REDACTED]:

[figure not shown]
[REDACTED]
[REDACTED]
[REDACTED]
[REDACTED]
[REDACTED]
[REDACTED]

The thresholds above have been selected to limit the risk to stop the study by chance and to avoid study extension in case the primary and first secondary objectives cannot be demonstrated at interim analysis or the planned [REDACTED] evaluable cases for the primary endpoint cannot be achieved in 3 seasons.

5.4.4.2 IDMC Recommendation

[Figure 5.1](#) illustrates the rules for IDMC recommendation based on the results of interim analyses and Sponsor's action upon the recommendation. More details will be made available in a separate SAP for IDMC and IDMC charter.

Figure 5.1: [REDACTED]

5.5 Determination of Sample Size and Power Calculation

A total of approximately 13,320 subjects will be enrolled: 100 subjects will be enrolled in the 2020-2021 NH influenza season in the open-label Sentinel Safety Cohort and 13,220 subjects in the main cohort will be enrolled over 3 subsequent influenza seasons with a randomization ratio of 1:1 for QIV-HD to QIV-SD.

Table 5.2: Planned sample size by vaccine and influenza season

Vaccine	Number of Subjects		
QIV-HD for open-label, Sentinel Safety Cohort	100		
Vaccine	Season 1 (NH)		
	Randomized	Immunogenicity Subset	Expanded safety analysis set (ESafAS)
QIV-HD			
QIV-SD			
Total			
Vaccine	Season 2 (SH)		
	Randomized	Immunogenicity	Expanded safety AS)
QIV-HD			
QIV-SD			
Total			
Vaccine	Season 3 (NH)		
	Randomized	Immunogenicity Subset	Expanded safety analysis set (ESafAS)
QIV-HD			
QIV-SD			
Total			
Vaccine	Season 3 (NH) Re-vaccination Cohort†		
	Randomized	Immunogenicity	Expanded safety S)
QIV-HD			
QIV-SD			
Total			
Overall Total	13,320 subjects with █ tested for immunogenicity*, █ for expanded safety, and 100 sentinel safety cohort subjects		

Abbreviations: NH, Northern Hemisphere; QIV-HD, high-dose quadrivalent influenza vaccine ; QIV-SD, standard-dose quadrivalent influenza vaccine ; SH, Southern Hemisphere

* Number of subjects who provide blood samples in Season 1 (NH) is greater than in Season 2 (SH) or Season 3 (NH) because unlike the Season 2 and 3 sera, which will be used for the descriptive immunogenicity results and █, Season 1 (NH) sera will also be used to demonstrate immunogenicity superiority.

† Approximately █ subjects from the Immunogenicity Subset of Season 1 (NH) will re-enroll in Season 3 (NH) to be evaluated for antibody persistence and re-vaccination immunogenicity endpoints. These subjects will not be part of the approximately █ subjects in Season 3 who are being followed for ILI surveillance and efficacy.

Table 5.3: Samples sizes for evaluation based on assessment method

Assessment Method	Number of Subjects
hemagglutination inhibition (HAI)	approximately █ subjects (all subjects in the Immunogenicity Subset)
seroneutralization (SN)	approximately █ subjects in Season 1's Immunogenicity Subset
enzyme-linked lectin assay (ELLA)	Approximately █ subjects in Season 1's Immunogenicity Subset

5.5.1 For efficacy assessments:

The sample size needed for the assessment of the primary objective of the study is expected to be approximately █ subjects and may be adjusted based on the blinded number of cases in order to maintain the likelihood of achieving approximately █ evaluable influenza cases from the PPASE meeting the primary endpoint.

These required numbers of evaluable influenza cases would provide at least █ power at final analysis to conclude on the primary objective under the following assumptions:

- The true rVE of QIV-HD to QIV-SD is █
- An overall one-sided Type I error rate 0.025 (█ spent at interim and final analysis, respectively)
- The lower bound of the CI of rVE should be > 5%
- An allocation ratio of QIV-HD to QIV-SD of 1:1
- An overall influenza attack rate of █ for the occurrence of an influenza case in the QIV-SD group (equivalent to an attack rate of █ across QIV-HD and QIV-SD groups in the PPASE given total number of evaluable cases is █)
- █ of enrolled subjects evaluable for the primary endpoint

Based on the same assumptions and using a more stringent █ threshold, the power for the first secondary objective at final analysis is expected at approximately █

If there is a need to extend the study to Season 4, number of subjects required will be re-calculated in a blinded manner. By way of illustration,

If the overall attack rate across 2 vaccine groups is █, to demonstrate the superior efficacy of QIV-HD over QIV-SD with the lower bound of █ CIs > █ and approximately █ power assuming the true rVE of QIV-HD to QIV-SD is █, 1:1 allocation ratio and █ of enrolled subjects evaluable the total number of subjects required is █. Additional █ subjects will be enrolled in Season 4. At the end of Season 4, █ cases would be expected to have occurred.

At least █ evaluable laboratory-confirmed influenza cases will be required for the interim analysis to be conducted. Such a number of cases would provide a power of approximately █,

to demonstrate up to the first secondary objective if the vaccine efficacy is [REDACTED] respectively, using one-sided alpha of [REDACTED].

For the assessment of the 2nd and 3rd confirmatory secondary efficacy objectives, the assumptions will be similar to those for primary objective except

- The lower bound of the CI for the corresponding rVE will be superior to 0%.
- The true rVE of QIV-HD to QIV-SD is [REDACTED] for each subset (ie, subjects 6 through 35 months of age against similar strains and subjects 6 through 24 months of age against any strains)
- [REDACTED] evaluable influenza cases ([REDACTED] of total cases) from each subset

For each objective, a [REDACTED] power will be achieved with a two-sided 97.5% CI and an [REDACTED] power will be achieved with a two-sided 95% CI.

5.5.2 For the immunogenicity assessments:

Approximately [REDACTED] subjects will be assessed for HAI immunogenicity in Season 1. Based on Phase II immunogenicity results from QHD04 and assuming [REDACTED] of non-evaluable subjects, with [REDACTED] evaluable subjects ([REDACTED] in each vaccine group), the study will have an overall [REDACTED] power to demonstrate the superiority for both HAI GMTs and seroconversion rates comparing QIV-HD to QIV-SD for all 4 strains with 1:1 allocation ratio ([Table 5.4](#)). The superiority margin is defined as 1 for GMTR and 0 for seroconversion rates for all 4 strains. The adjustment for alpha is not needed as the superiority for immunogenicity is concluded only when the superiority is demonstrated in both HAI GMTs and seroconversion rates for all 4 strains.

Table 5.4: Power to demonstrate superiority for immunogenicity

Strain	Endpoint	Estimates		Power (%)
		Expected seroconversion rate in QIV-HD	Expected seroconversion rate in QIV-SD	
A/(H1N1)-like strain	Seroconversion rate			
A/(H3N2)-like strain	Seroconversion rate			
B/(Victoria lineage)-like strain	Seroconversion rate			
B/(Yamagata lineage)-like strain	Seroconversion rate			
		Expected GMT ratio (QIV-HD/QIV-SD)	Expected SD (log10 titer)	
A/(H1N1)-like strain	GMT			
A/(H3N2)-like strain	GMT			
B/(Victoria lineage)-like strain	GMT			
B/(Yamagata lineage)-like strain	GMT			
Overall power				

